5.3. Lifestyle Considerations

5.3.1. Meals and Dietary Restrictions

Patients should follow their study doctor's advice regarding adherence to a low Cu diet.

ALXN1840 will be administered in the fasted state (1 hour before or 2 hours after meals) and will be taken with approximately 240mL of water.

5.3.2. Restrictions Relating to the Liver Biopsy

Prior to biopsy and following biopsy, the guidelines and restrictions apply ([Rockey, 2009](#)):

- Antiplatelet medications should be discontinued a minimum of 10 days before liver biopsy.
- Anticoagulant medications should be discontinued prior to liver biopsy. Warfarin should generally be discontinued at least 5 days prior to liver biopsy. Heparin and related products should be discontinued 12 to 24 hours prior to liver biopsy. Oral agents, including rivaroxaban, dabigatran, apixaban, and edoxaban, should be discontinued a minimum of 72 hours before liver biopsy ([Douketis, 2019](#)).
- Antiplatelet therapy may be restarted 72 hours after liver biopsy.
- Warfarin may be restarted 24 hours after liver biopsy.

5.4. Screen Failures

Screen failures are defined as patients who consent to participate in the clinical study but are not subsequently assigned to study drug. A minimal set of screen failure information is required to ensure transparent reporting of screen failure patients to meet the Consolidated Standards of Reporting Trials (CONSORT) publishing requirements and to respond to queries from regulatory authorities. Minimal information includes demography, screen failure details (eg, failed eligibility criteria), and any serious adverse event (SAE) occurring during the Screening Period.

Individuals who do not meet the criteria for participation in this study (screen failure) may be rescreened up to 2 times after agreement on required repeated assessments with the Alexion Medical Monitor.

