2.3.1. Risk Assessment

Details of the potential risks and mitigation strategy are provided in [Table 3](#). Further information on ALXN1840 is available in the IB.

Table 3: Potential Risks and Mitigation Strategy

Potential Risk of Clinical Significance	Summary of Data/Rationale for Risk	Mitigation Strategy
ALXN1840		
Anemia	Anemia has been observed in patients with WD, attributed to overtreatment and resultant Cu depletion, see the IB	Monitoring complete blood count Dose modification (Section 6.6) or discontinuation (Section 7)
Dose-dependent elevations in transaminases (ALT and AST)	Generally mild to moderate in severity, asymptomatic and reversible with dose adjustments were reported, usually after 3-6 weeks of treatment. Results obtained from studies of ALXN1840 and ammonium tetrathiomolybdate in patients with WD; see the IB	Regular monitoring of liver function tests Dose modification (Section 6.6) or discontinuation (Section 7)
Low white blood cell count (leukopenia, bone marrow toxicity)	Leukopenia and bone marrow toxicity (myelosuppression) have been observed in patients with WD, attributed to overtreatment and resultant Cu depletion. Results obtained from studies of ALXN1840 and ammonium tetrathiomolybdate in patients with WD; see the IB	Dose modification (Section 6.6) or discontinuation (Section 7)
Study Procedures and Other		
Liver biopsy: bleeding, infection, liver laceration, pneumothorax, gallbladder injury	Overall rate of serious complications is approximately 1% and mortality at 0.2% Pain is most common complication with one quarter of patients experiencing right upper quadrant or shoulder pain, most common serious complication is bleeding with hemodynamic compromise occurring in 0.01% to 0.5% of cases and includes intraperitoneal hemorrhage, hematoma, and/or hemobilia. Additional complications include but are not limited to transient bacteremia, bile peritonitis, organ injury including pneumothorax (Reddy, 1997 ; Seeff, 2010 ; West, 2010 ; Boyum, 2016)	Abdominal ultrasound is required prior to biopsy to confirm adequate visualization of liver and adjacent structures (Section 5.1) Obese patients (BMI >30 kg/m ²) will be excluded from participating in the study (Section 5.1) Restrictions on antiplatelet and anticoagulant medications (Section 5.3.2) Patients must have a PT-INR < 1.5 (Section 5.2)

Potential Risk of Clinical Significance	Summary of Data/Rationale for Risk	Mitigation Strategy

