8. STUDY ASSESSMENTS AND PROCEDURES

- Study procedures and their timing are summarized in the SoAs ([Table 1](#) and [Table 2](#)). Protocol waivers or exemptions are not allowed.
- Immediate safety concerns should be discussed with Alexion immediately upon occurrence or awareness to determine if the patient should receive study drug.
- Adherence to the study design requirements, including those specified in the SoAs, is essential and required for study conduct.
- All screening evaluations must be completed and reviewed to confirm that potential patients meet all eligibility criteria. The Investigator will maintain a screening log to record details of all patients screened and to confirm eligibility or record reasons for screening failure, as applicable.
- Liver biopsy is the last pre-dose baseline procedure to be completed and must be completed within 14 days prior to the first dose of ALXN1840.
- Procedures conducted as part of the patient's routine clinical management (eg, blood count) and obtained before signing of the ICF may be utilized for screening or baseline purposes provided the procedures met the protocol-specified criteria and were performed within the time frame defined in the SoA ([Table 1](#)).
- Details of the maximum amount of blood to be collected from each patient over the duration of the study are provided in the laboratory manual and ICF.

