8.3. Adverse Events and Serious Adverse Events

AEs will be reported to the Investigator or qualified designee by the patient (or, when appropriate, by a caregiver, surrogate, or the patient's legally authorized representative).

The Investigator and any qualified designees are responsible for detecting, documenting, and recording events that meet the definition of an AE or SAE and remain responsible for following up AEs that are serious, considered related to the study drug or study procedures, or that caused the patient to discontinue the study drug (see [Section 7](#)).

Definitions and procedures for recording, evaluating, follow-up, and reporting AEs and SAEs are outlined in [Section 10.3](#).

8.3.1. Time Period and Frequency for Collecting Adverse Event and Serious Adverse Event Information

All AEs will be collected from the signing of the informed consent until the follow-up visit at the time points specified in the SoAs ([Table 1](#) and [Table 2](#)).

All SAEs will be recorded and reported to Alexion or designee within 24 hours, as indicated in [Section 10.3](#). The Investigator will submit any updated SAE data to Alexion within 24 hours of it being available.

Investigators are not obligated to actively seek AEs or SAEs after conclusion of the study participation. However, if the Investigator learns of any SAE, including a death, at any time after a patient has exited the study, and he/she considers the event to be reasonably related to the study drug, the Investigator must promptly notify Alexion Global Drug Safety (GDS).

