6.2. Data Sets in the Treatment Period

6.2.1. Safety Analysis Set in the Treatment Period

Safety Analysis Set in the Treatment Period is defined as all patients who receive at least 1 dose of treatment in the Treatment Period. This population will be used for the safety analyses in the Treatment Period.

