7.3. Safety Analyses

All safety analyses will be conducted on the Safety Analysis Set in the Treatment Period. Safety analyses will include all AEs, ECGs, clinical laboratory data, physical examinations, and vital sign measurements using descriptive statistics. By-patient listings will also be provided. No formal hypothesis testing is planned.

The verbatim terms as reported in the CRF by Investigators to identify AEs will be coded using MedDRA version 23.0 or higher and summarized by primary SOC and PT.

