7.3.2.1. Overall Summary of Adverse Events

An overall summary of TEAEs will be presented, including the number of events and the number and percentage of patients experiencing AEs. Percentage will be calculated as $n / N \times 100$, where n is the number of patients with events and N is the number of patients in the Safety Analysis Set. The summary will include categories indicating how many events are TEAEs, treatment-emergent SAEs, and treatment-emergent non-SAEs.

A patient-level listing of all TEAEs will be presented. Separate listings will be produced for SAEs, AEs leading to study drug withdrawal, AEs resulting in death, AEs leading to withdrawal from the study, and pre-treatment AEs (PTAEs).

7.3.2.2. Adverse Events and Serious Adverse Events by System Organ Class and Preferred Term

The number of TEAEs and the number and percentage of patients with events will be presented by SOC and PT. Patients are counted once in each SOC and PT. Percentages will be based on the Safety Analysis Set. The SOCs will be listed in descending frequency as will PTs' within each SOC. If needed, PTs will also be ordered alphabetically.

Treatment-emergent SAEs, treatment-emergent non-SAEs, TEAEs leading to withdrawal of study drug, TEAEs leading to death, and PTAEs will be summarized using the same approach.

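### Every planned AE table, including the pre-treatment one, requires a dose of study drug, so a baseline-biopsy complication that prevents dosing is not tabulated (minor)

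*Protocol*

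**What the plan says.** **Order of events.** Protocol 1.3 places the baseline biopsy after all other screening work, once eligibility is confirmed. Protocol 8 adds: "Liver biopsy is the last pre-dose baseline procedure to be completed".

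**Status of a patient not dosed.** Protocol 5.4: "Screen failures are defined as patients who consent to participate in the clinical study but are not subsequently assigned to study drug". SAP 6.1 instead counts as enrolled anyone who consented and passed the eligibility criteria. A patient biopsied but never dosed fits both descriptions.

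**Collection.** Protocol 5.4, on screen failures: "Minimal information includes demography, screen failure details (eg, failed eligibility criteria), and any serious adverse event (SAE) occurring during the Screening Period". Protocol 8.3.1: "All AEs will be collected from the signing of the informed consent until the follow-up visit". The same section requires SAEs to reach the sponsor within 24 hours.

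**Analysis.** SAP 6.2.1 gives the Safety Analysis Set as "defined as all patients who receive at least 1 dose of treatment in the Treatment Period". SAP 7.3: "All safety analyses will be conducted on the Safety Analysis Set in the Treatment Period". SAP 7.3.2.2 bases AE percentages on that set and then adds: "TEAEs leading to death, and PTAEs will be summarized using the same approach".

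**Disposition.** SAP 7.1.1 counts reasons for screen failure, including reasons other than eligibility. It also lists screen failures and lists all enrolled patients with their reason for discontinuation. None of these outputs is said to carry AEs.

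**Expected risk.** Protocol 2.3.1, Table 3, on liver biopsy: "Overall rate of serious complications is approximately 1% and mortality at 0.2" (both figures are percentages). Protocol 2.3.3 names the biopsy among the risks it judges to be justified.

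**The concern.** The PTAE table is the natural place to report harm from the baseline biopsy, since that harm arises before any drug is given. But the table can hold only patients who went on to take drug. The omission is selective: the events removed are those bad enough to stop the patient from starting treatment, and the milder ones stay. The direction of the bias is therefore known, and it is downward.

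What is at stake is the reported safety of the procedure. The drug safety tables and the primary analysis are not affected. The biopsy is done for research in patients already stable enough to qualify, and the protocol argues that its risk is acceptable. A reader of the study report would expect the pre-treatment table to show how the first round of biopsies went.

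**Working it through.** **1. Follow one patient through the plan.** The patient consents, meets all criteria, has the baseline biopsy, suffers a serious complication and is never dosed.

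| Output | Population rule | Patient included? |
|---|---|---|
| TEAE tables (SAP 7.3.2) | Safety Analysis Set; onset on or after first dose | No, and rightly so |
| PTAE table (SAP 7.3.2.2) | Same approach as the TEAE table, so Safety Analysis Set | No |
| SAE, death and PTAE listings (SAP 7.3.2.1) | Not stated; SAP 7.3 points to dosed patients | Unclear |
| Screen-failure reasons and listing (SAP 7.1.1) | Screen failures | Yes under Protocol 5.4; AE content not specified |
| Listing of enrolled patients (SAP 7.1.1) | Enrolled | Yes under SAP 6.1; AE content not specified |

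The exclusion comes from the dosing rule in the SAP. Protocol 5.4 shows that the SAE is captured, and the SAP then gives it no table.

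**2. Number of baseline biopsies.** Protocol 9.2 plans 24 evaluable patients with 15% dropout: 24 / (1 - 0.15) = 28.2, which agrees with its figure of about 28. I take n = 28 baseline biopsies. This is an assumption, because patients biopsied but not dosed might come on top of that number.

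**3. Serious complications of any kind, at the protocol's 1%.**
- Expected number: 28 x 0.01 = 0.28.
- Chance of at least one: 1 - 0.99^28 = 24.5%.
- If the true rate were 0.5% or 2% (assumed range), the chance would be 1 - 0.995^28 = 13.1% or 1 - 0.98^28 = 43.2%.

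**4. Serious complications that go untabulated.** The relevant event is a serious complication in a patient who is then never dosed. The documents do not give the share f of such patients who are not dosed, so I show a range. Formula: 1 - (1 - 0.01 x f)^28.
- f = 25%: 1 - 0.9975^28 = 6.8%.
- f = 50%: 1 - 0.995^28 = 13.1%.
- f = 100%: 1 - 0.99^28 = 24.5%.

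**5. Deaths, at the protocol's 0.2%.** A patient who dies of the biopsy before the first dose cannot enter a dosed-only table, so no share is needed. Taking the death to occur before dosing, the chance of at least one is 1 - 0.998^28 = 5.5%.

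**6. What one case does to the table (assumed illustration).** Suppose 29 patients are biopsied, one has a serious complication and is never dosed, and the other 28 are dosed without a serious event. Exact (Clopper-Pearson) 95% intervals:
- Planned PTAE table: 0/28 = 0% (0 to 12.3%).
- Table over all biopsied patients: 1/29 = 3.4% (0.1% to 17.8%).

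The intervals overlap widely, as they must at this size. What changes is whether the event appears in a table at all.

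**The case against.** The case on the other side is substantial.

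- **A dosed-only set is the usual choice for drug safety**, and the safety objective concerns ALXN1840. Measuring biopsy risk is not a study objective, and about 28 biopsies cannot confirm or refute a 1% rate. This stands. It is why the TEAE tables should stay as they are and why the point is minor. It does not explain why a table of events before treatment should require treatment.
- **The data are not lost.** A reader might infer that the plan hides biopsy harm. The documents do not support that: AEs are collected from consent, SAEs go to the sponsor within 24 hours, the monitoring committee is active before the Treatment Period (Protocol 9.5), and the patient appears in disposition outputs. The gap is in tabulation only.
- **Protocol 5.4 does not limit collection to SAEs.** It can be read that way, but it describes a minimum, and 8.3.1 already asks for all AEs from consent. Protocol 10.3 does define an AE by reference to study drug use, which sits awkwardly with collection from consent. However, 8.3.1 and the naming of screening SAEs in 5.4 make the intent clear enough.
- **Not every biopsy event is missed.** Events in patients who are later dosed appear as PTAEs, and Week 48 biopsy events fall within the TEAE definition. It would be wrong to read 24.5%, or the roughly 7 of 28 patients expected to have pain (28 x 0.25, from Table 3's one quarter), as harm missing from the tables. Those figures count any such complication. The 24.5% applies only as the upper end, when every patient with a serious complication goes undosed.
- **The listings might close the gap.** Listings of SAEs, deaths and PTAEs are planned, and Protocol 9.4 says all variables are listed by patient. Their population is not stated, though, and a listing gives no denominator.

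**Conclusion.** The point holds, with modest weight. By the SAP's own rules, a patient whose baseline-biopsy complication prevents dosing is in no AE table, and the tabulated pre-dose biopsy harm is biased downward. The expected number of serious baseline complications is 0.28. The chance that at least one is untabulated runs from about 7% to 25% over assumed undosed shares of 25% to 100%, and the chance of at least one death is about 5.5%. These figures rest on the protocol's quoted rates, on 28 independent biopsies, and on a share that the documents do not give. The stronger conclusion, that such harm would go unrecorded or unreported, does not follow from the documents. Severity: minor.

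**What to change.** **SAP 6 and 7.3.2.** Add one table of AEs and SAEs with onset from the baseline biopsy to the first dose, or to screen failure or withdrawal for a patient never dosed. Its denominator is all consented patients who had the baseline biopsy. State that the SAE, death and PTAE listings cover all consented patients. Keep the TEAE tables on the Safety Analysis Set.

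**Protocol 5.4 and SAP 6.1.** Reconcile the two labels, so that a patient biopsied but not dosed is either a screen failure or enrolled. In 5.4, add that all AEs are kept for a screen failure who had the biopsy. This only clarifies what 8.3.1 already requires.

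**Cost.** One denominator, one table and two or three sentences. No new visits or data are needed. The reported biopsy risk may look slightly worse.

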6. STUDY DRUG

Study drug is defined as any investigational drug intended to be administered to a study patient according to the study protocol, ie, ALXN1840.

6.1. Study Drugs Administered

Details of the study drug to be administered in this study are detailed in [Table 5](#).

Table 5: Study Drugs Administered

Drug Name	ALXN1840
Type	Drug
Dose Formulation	White, round, delayed-release tablet
Unit Dose Strength(s)	15 mg
Dosage Level(s)	15 mg daily up to 30 mg daily
Route of Administration	Oral
Use	Experimental
IMP and NIMP	IMP
Sourcing	Provided centrally by Alexion
Packaging and Labeling	ALXN1840 will be provided in treatment kits that will each have a unique identification number and be packaged and labelled in accordance with all applicable regulatory requirements. At a minimum, the treatment kit label will provide the following information: study Sponsor identification, batch number, directions for use, required storage conditions, caution statements (including “New Drug-Limited by Federal Law to Investigational Use” language), study identification, and expiry date.
Current/Former Name(s) or Alias(es)	bis-choline tetrathiomolybdate

Abbreviations: IMP = investigational medicinal product; NIMP = Noninvestigational medicinal product

6.2. Preparation/Handling/Storage/Accountability

- The ALXN1840 treatment kits must be stored at refrigerated conditions, 2°C to 8°C (36°F to 46°F).
- The Investigator or designee must confirm appropriate temperature conditions have been maintained during transit for all study drug received and any discrepancies are reported and resolved before use of the study drug.
- Only patients enrolled in the study may receive study drug. Appropriately trained employees of the study site will instruct patients on how to correctly dose themselves with ALXN1840 at home.
- All study drug must be stored in a secure, environmentally controlled, and monitored (manual or automated) area in accordance with the labeled storage conditions with access limited to the Investigator and authorized site staff.
- The Investigator, institution, or the head of the medical institution (where applicable) is responsible for study drug accountability, reconciliation, and record maintenance (ie, receipt, reconciliation, and final disposition records).

- Further guidance and information for the final disposition of unused study drug are provided in the Pharmacy Manual.

6.3. Measures to Minimize Bias: Randomization and Blinding

- There is no randomization and blinding of patients in this study, because it is a single-arm, open-label study.
- This study is only pathologist-blinded for the assessments of liver histology samples.
- Study drug will be dispensed at the study visits summarized in the SoAs ([Table 1](#) and [Table 2](#)).

6.4. Study Drug Compliance

Compliance with ALXN1840 will be assessed by the study team at each study visit. Compliance will be assessed by direct questioning during the site visits and documented in the source documents and case report form (CRF) and checked against the medication returned by the patient. Any deviation from the prescribed dosing regimen including extra doses, missed doses and drug interruptions will be recorded in the electronic data capture (EDC) system.

Patients who take 80% or more of the prescribed doses of ALXN1840 in the first 48 weeks of the study will be considered to have shown acceptable compliance.

Reasons for not following study treatment administration as described in the protocol should be clearly recorded in the source documents.

Once compliance with study drug has been calculated, patients will be dispensed new ALXN1840 to cover dosing requirements until the next in-clinic visit if required.

A record of the number of ALXN1840 tablets dispensed to and taken by each patient must be maintained and reconciled with study drug and compliance records. Study drug start and stop dates, including dates for drug delays and/or dose reductions will also be recorded in the CRF.

6.5. Concomitant Therapy

Any medication or vaccine (including over-the-counter or prescription medicines, vitamins, and/or herbal supplements or other specific categories of interest) taken within 30 days prior to signing informed consent and throughout the duration of the study will be recorded in the source documents and on the appropriate CRF along with:

- Reason for use
- Dates of administration including start and end dates
- Dosage information including dose and frequency

Medications specific for WD taken at any time prior to the study will also be recorded.

Patients may continue medications required to treat existing medical conditions as long as they are not anticipated to interfere with the conduct or outcome of the study. Patients should avoid starting or stopping medications and all potential medication changes should be reviewed by the Investigator to ensure changes are not expected to interfere with the outcome of the study.

The guidelines provided below are to be used by the Investigator, the study staff, and the patient to safeguard patient safety while maintaining data integrity.

Use of the following medications or contrast media is not prohibited; however, if used, this therapeutic change must be clearly documented as a concomitant medication. Please contact the Alexion Medical Monitor with questions. Refer to the current IB for potential inhibitory effect of ALXN1840 on the metabolism of certain drugs that are substrates of cytochrome P450 enzymes (eg, CYP2C9 and CYP2B6).

- Gadolinium- and iodine-containing contrast media are known to interfere with PK/PD tests on Mo. Gadolinium- and iodine-containing contrast media are requested not to be used within the 96 hours prior to Mo testing.
- Barium-containing contrast media are known to interfere with tests on Cu. Barium-containing contrast media are requested not to be used within the 96 hours prior to Cu testing.
- Acetaminophen/paracetamol must be limited to ≤ 1 g per day.

The following medications are prohibited during the study:

- Estrogens may interfere with biliary Cu excretion. Patients must not initiate estrogen therapy or estrogen-containing contraception on or after the Day 1 visit. Detailed guidance on allowed contraceptive methods and medication are provided in [Section 10.4](#).
- Standard of care medications for WD (trientine, penicillamine, and zinc) must be discontinued prior to the start of the Treatment Period (Day 1) with ALXN1840 and should not be used throughout the duration of study treatment.
- Vitamin E has been used as an adjunctive therapy in WD treatment regimens. Patients must not initiate use of vitamin E during the study.
- Patients must not use vitamins and/or minerals containing Cu, zinc, iron, or Mo.

